2.5.4 Sensitivity analyses for primary endpoint/estimand

Sensitivity analyses on the primary endpoint will be performed where missing central lab hemoglobin data will be replaced by available local lab data collected at the same visit. The logistic regression model and simple proportion without any covariate adjustment which are used for primary efficacy analysis will be performed for these sensitivity analyses.

Additional sensitivity analyses on the primary analysis will be performed:

- Considering the need for transfusion derived from imputation with imputed values ≤ 7 g/dL (≤ 6 g/dL for Chinese population) to be sufficient to warrant a transfusion.

This means assuming that none of the patients with imputed hemoglobin between 9 g/dL and 7 g/dL (between 8 g/dL and 6 g/dL for Chinese patients) would have presented symptoms warranting transfusion.

[figure not shown]
- Considering administered transfusions.

2.5.5 Supplementary analyses

A supplementary estimand considering the use of rescue therapy (as defined in the study protocol) under intercurrent event as treatment failure, for the purpose of efficacy assessment, will be performed. The supplementary estimand will have the same population, treatment of interest, and summary measure as the primary estimand. The logistic regression model or simple proportion which is used for primary efficacy analysis will be performed for these supplementary analyses (see [Section 2.5.2.2](#)). For this analysis the following will be considered:

- Participant meeting the criteria for administration of RBC transfusions or having received a transfusion between Day 14 and Day 168 will be considered treatment failures.
- Use of rescue medication during the core treatment period between Day 1 and Day 168 will be considered treatment failures. The rescue therapy will be used for analysis as it is reported by the investigator under the subcategory of Rescue Medications/Therapy on the Concomitant Medication, Surgical and Medical Procedures CRF page.
- Discontinuations of study medication for any reason will be handled with treatment policy strategy.

The marginal proportions /response probabilities will be estimated using a logistic regression or simple proportion as for the primary variable ([Section 5.2.2.2](#)).

2.6 Analysis of secondary endpoints/estimands

2.6.1 Secondary endpoints/secondary estimands

Descriptive statistics and summaries on the secondary endpoints based on FAS will be provided.

2.6.1.1 Proportion of participants achieving sustained hemoglobin levels ≥ 12 g/dL in the absence of red blood cell transfusions

The number and percentage of patients reaching a fixed threshold ≥ 12 g/dL on three out of four measurements taken at the visits occurring in last six weeks (from Day 126 to Day 168).

The analysis of the secondary endpoint will be a logistic regression and simple proportion to estimate the response probability. The covariates in logistic regression include sex, age (indicator of age ≥ 45 years), an indicator variable of baseline hemoglobin ≥ 8 g/dL and an indicator of transfusion dependence prior to starting study treatment.

This means that the proportion of responders will be derived from the estimated marginal probabilities derived from the model fit as the mean of the individual logistic regression model predictions, together with the 95% confidence intervals, where the standard error will be derived by the bootstrap method ([Steingrímsson et al 2017](#)).

The marginal proportions /response probabilities will be estimated using a logistic regression or simple proportion as for the primary variable ([Section 5.2.2.2](#)).

2.6.1.2 Transfusion Avoidance

The number and percentage of patients not receiving and not meeting the criteria for administration of packed RBC transfusions in the core treatment period will be summarized overall and by transfusion history during the last 6 months prior to starting study treatment (i.e. transfusion received/not received). The number and percentage of patients not receiving and not meeting the criteria for administration of any RBC transfusion between Day 14 and Day 168 will be summarized overall and by transfusion during the last 6 months prior to start of study treatment (i.e. transfusion received/not received). Time to first packed RBC transfusion from start of study treatment (Day 1) will be plotted using Kaplan Meier curves for overall and by transfusion during the last 6 months prior to start of study treatment (i.e. transfusion received/not received).

For RBC transfusions during the study, the hemoglobin level criterion deemed appropriate by the investigator for requiring the transfusion and signs and symptoms reported prior to receiving transfusion will be summarized. The information will be summarized based on the 'Transfusion-during the study' CRF page.

Transfusion avoidance will be evaluated as the proportion of participants not receiving and not meeting the criteria of administration of RBC transfusion between Day 14 and Day 168, and similarly to the estimation applied to the primary estimand ([Section 2.5.2](#)) by means of standardized marginal proportions. The logistic regression model will include sex, age (indicator of age ≥ 45 years), an indicator variable of baseline hemoglobin ≥ 8 g/dL and an indicator of transfusion dependence.

The marginal proportions /response probabilities will be estimated using a logistic regression or simple proportion as for the primary variable ([Section 5.2.2.2](#)).

2.6.1.3 Change from baseline in hemoglobin levels

Estimation of change from baseline in hemoglobin levels is under the hypothetical situation in which participants would not have received transfusions on iptacopan treatment. For this analysis, if a participant had a transfusion during the core treatment period then the hemoglobin values 30 days following the transfusion will be considered missing and hemoglobin data will be imputed. In practice, this would be implemented considering participants on iptacopan to have data imputed assuming missing at random. This will be accomplished by the use of imputed values ([Section 2.5.3](#)).

The model for the estimation is a mixed model for repeated measures (MMRM) considering an unstructured covariance structure. The model will include transfusion dependence, age (indicator of age ≥ 45 years), sex, visit, baseline hemoglobin and the interactions between visits and baseline levels. The treatment estimates will be computed as the mean changes from baseline corresponding to the average of hemoglobin levels measured in the last 6 weeks of treatment (that is the visits occurring between Day 126 and Day 168).

The estimated least square mean estimate of the treatment effect and the associated 95% confidence interval will be plotted over time. Refer to [Section 5.2.3](#) for detail.

2.6.1.4 Change from baseline in FACIT-Fatigue scores

The endpoint consists of changes from baseline in scores of fatigue using the FACIT-Fatigue questionnaire where baseline is defined as in [Section 2.1.1.2](#). As for the other endpoints, the longitudinal model will be a repeated measures model including test scores collected at all visits.

The model for the estimation is a MMRM considering an unstructured covariance structure. The model will include transfusion dependence, age (indicator of age ≥ 45 years), sex, visit, baseline in scores of fatigue and the interactions between visits and baseline levels. The estimation will be an average of treatment estimates derived for visits occurring between Day 126 and Day 168. The estimated least square mean estimate of the treatment effect and the associated 95% CI will be plotted over time.

2.6.1.5 Change from baseline in reticulocyte counts

The estimation of the change from baseline in absolute reticulocyte counts will be derived from a MMRM including data collected throughout the study and where baseline is defined as the value on Day 1. The model for the estimation is a MMRM considering an unstructured covariance structure. The model will include transfusion dependence, age (indicator of age ≥ 45 years), sex, visit, baseline reticulocyte counts and the interactions between visits and baseline levels.

The estimation will use the average of model derived estimates obtained at visits occurring between Day 126 and Day 168. The estimated least square mean estimate of the treatment effect and the associated 95% CI will be plotted over time.

2.6.1.6 Percent change from baseline in LDH

The treatment effect on percent change from baseline in LDH will be assessed using a MMRM of log transformed ratio to baseline based on all observations collected during follow-up. The model for the estimation is a MMRM considering an unstructured covariance structure. The model will include transfusion dependence, age (indicator of age ≥ 45 years), sex, visit, log-transformed baseline LDH and the interactions between visits and log-transformed baseline levels. Estimation will be derived based on the average of the log transformed ratio from baseline estimated between Day 126 and Day 168. Percentage change from baseline (reduction or increase) and associated 95% confidence intervals will be plotted for treatment effect over time.

2.6.1.7 Rates of Major Adverse Vascular Events (MAVE)

Information of MAVEs as collected on the 'MAVE' CRF page will be used for analysis and the information will also be reported as a part of the adverse event summaries. The number and percentage of participants with treatment-emergent (MAVEs) in the core treatment and extension treatment periods will be summarized by reported term. The information on MAVEs (including those in the screening period) will be listed and the treatment emergent events will be flagged.

Based on FAS, the estimation of rates of MAVEs will be carried out using a negative binomial model. Due to the expected low frequency of occurrences, no covariates are planned to be included. Following the treatment policy strategy for handling treatment discontinuations, the offset variable will be defined as the time from Day 1 till minimum (end of study, end of core treatment period).

If the model fails to converge, then a Poisson model without covariates will be fitted. If both negative binomial and Poisson model fail to converge, the Wilson ([Miettinen and Nurminen, 1985](#)) method will be implemented to produce 95% CI.

2.6.1.8 Rates of clinical breakthrough hemolysis

Information of clinical breakthrough events as collected on the 'Breakthrough Hemolysis' CRF page will be used for analysis and the information will also be reported as a part of the adverse event summaries. The number and percentage of patients experiencing treatment emergent clinical breakthrough hemolysis events in the core treatment and extension treatment periods will be summarized. The information on whether the patient received packed-RBC transfusions and the quantity of packed-RBC transfusions due to clinical breakthrough hemolysis will be summarized. Clinical breakthrough hemolysis events (including those in the screening period) will be listed and the treatment emergent events will be flagged.

Based on FAS, the estimation of rates of clinical breakthrough hemolysis will be carried out using a negative binomial model. The model will include the following covariates: transfusion dependence, age (indicator of age ≥ 45 years), sex, indicator variable of baseline hemoglobin ≥ 8 g/dL. Following the treatment policy strategy for handling treatment discontinuations, the offset variable will be defined as the time from Day 1 till minimum (end of study, end of core treatment period).

If the above model fails to converge due to low frequency of occurrences, then the model will be run considering no covariates in the negative binomial model. If the model fails to converge, then a Poisson model without covariates will be fitted. If both negative binomial and Poisson model fail to converge, the Wilson ([Miettinen and Nurminen, 1985](#)) method will be implemented.

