4.1 Rationale for study design

CLNP023C12301 is a multicenter, single arm, open-label study designed to evaluate the efficacy and safety of iptacopan at a dose of 200 mg b.i.d. orally in adult PNH patients who are naive to any complement therapy, including anti-C5 antibody. A single arm design is chosen for this study for the following reasons:

- The study is the pivotal study to support the registration of iptacopan as treatment of PNH in countries where anti-C5 treatment (current SoC for PNH in countries where approved) is not available. As such, an active-comparator controlled design is not possible. The study will also provide supportive data for the global registration of iptacopan which will be based on a randomized controlled pivotal phase 3 trial comparing iptacopan vs anti-C5 treatment.
- A placebo-controlled design is deemed unethical with the compelling evidence of benefit of iptacopan in patients with PNH based on the IAs of the two Phase 2 PNH studies (LNP023X2201, LNP023X2204). Furthermore, a placebo arm is not considered appropriate with severe, life threatening diseases such as PNH.

The single arm, open-label design is widely used in rare diseases due to challenges associated with conducting studies in these patient populations (Bell and Smith 2014). Several measures have been included in the study design to minimize biases associated with this single arm open-label design, including

- Primary and majority of secondary, efficacy endpoints are objectively measured via laboratory assessments (i.e. hematological response parameters, hemoglobin, LDH, reticulocytes, transfusion avoidance and BTH).
- Protocol-specific guidelines (see Section 8.3.2) are defined to reduce potential bias due to events (such as transfusions) that may affect the main endpoints.

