6.4 Treatment blinding

Treatment will be open to participants, Novartis Clinical Trial Team (CTT), the investigator staffs and persons performing the assessments. The CTT will have access to standard reports of patient profiles and other listings necessary to fulfill data review. There will be an Independent Statistician and an Independent Programmer who will provide analyses of safety data for the review of the members of the DMC at periodic intervals.

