8.3.3 Breakthrough hemolysis

The occurrence of BTH will be monitored continuously during the Core treatment period.

The criteria for clinical breakthrough is defined in [Table 8-3](#) below if either one of the two clinical criteria is met, in presence of the laboratory evidence of intravascular hemolysis and should be reported in the 'Breakthrough hemolysis' CRF page in addition to the AE page.

In contrast to clinical breakthrough as defined, the isolated laboratory evidence of increased intravascular hemolysis, without meaningful decrease in hemoglobin and without other clinical signs or symptoms of hemolysis (per [Table 8-3](#)) is defined as subclinical breakthrough hemolysis, and should **not** be reported in the 'Breakthrough hemolysis' CRF page.

Table 8-3 Breakthrough hemolysis definition

	Clinical criteria		Laboratory criteria
	Hemoglobin levels	Signs or symptoms	LDH level
Clinical breakthrough*	Decrease equal to or more than 2 g/dL (compared to the latest assessment, or within 15 days)	Gross hemoglobinuria, painful crisis, dysphagia or any other significant clinical PNH-related signs & symptoms	> 1.5-times ULN and increased as compared to the last 2 assessments
Subclinical breakthrough	Decrease less than 2 g/dL (compared to the latest assessment, or within 15 days)	No clinical signs or symptoms, except moderate hemoglobinuria	> 1.5-times ULN and increased as compared to the last 2 assessments

LDH: lactate dehydrogenase; ULN: Upper Limit of Normal;

*The breakthrough is defined clinical if either one of the two clinical criteria is demonstrated, in presence of laboratory evidence of intravascular hemolysis (LDH level)

During the Extension treatment period, breakthrough hemolysis will be monitored continuously until the end of study visit following the same criteria and guidance described above.

The assessment could be based on local laboratory results. However, the investigator should also collect at the same time a sample for the central laboratory assessment of hemoglobin and LDH, whenever possible.

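### The breakthrough-hemolysis rate rests on the site's CRF page alone, with no visible check against the Hb and LDH values already collected at every Core visit

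*SAP*

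**What the plan says.** - **Event source.** SAP 2.6.1.8 begins "Information of clinical breakthrough events as collected on the" and, after naming the breakthrough page, continues "CRF page will be used for analysis and the information will also be reported as a part of the adverse event summaries". A negative binomial model is fitted to those events.
- **Who reports.** Under Protocol 8.3.3 a clinical event "should be reported in the 'Breakthrough hemolysis' CRF page in addition to the AE page". Subclinical events must not go on the breakthrough page. The assessment may rest on local results, with a central sample where possible.
- **Definition.** Table 8-3 requires LDH above 1.5 times ULN and higher than at the last two assessments, plus at least one of two clinical limbs. One limb is hemoglobin: "Decrease equal to or more than 2 g/dL (compared to the latest assessment, or within 15 days". The other is clinical: "Gross hemoglobinuria, painful crisis, dysphagia or any other significant clinical PNH-related signs & symptoms".
- **Blinding.** Protocol 6.4: "Treatment will be open to participants, Novartis Clinical Trial Team (CTT), the investigator staffs and persons performing the assessments".
- **Bias defence.** Protocol 4.1 offers as a measure against single-arm, open-label bias: "Primary and majority of secondary, efficacy endpoints are objectively measured via laboratory assessments (i.e. hematological response parameters, hemoglobin, LDH, reticulocytes, transfusion avoidance and BTH".
- **Checks.** SAP Table 5-1 lists BTH as secondary estimand 7 without a sensitivity analysis. SAP 2.6.3 and 2.6.4 add none for it.

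**The concern.** Protocol 4.1 implies that the BTH count is protected by laboratory measurement. In the SAP, an event enters the count only if someone who knows the treatment opens a CRF page. If an episode meets the hemoglobin and LDH criteria but is judged subclinical or overlooked, that page holds no trace of it. Conversely, an entered event that misses the LDH criterion is counted without challenge.

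The plan handles the same problem differently for transfusion. Under Protocol 12.4.1 and SAP 2.5.1, a participant who met the transfusion criteria counts as a failure even if no transfusion was given. The version based on administered transfusions is a sensitivity analysis (SAP 2.5.4). BTH also has written criteria but has no comparable treatment.

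At stake are the accuracy of a secondary rate in a pivotal single-arm study and the weight that Protocol 4.1 can bear for that endpoint.

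**Working it through.** The documents give no expected BTH rate, count, threshold or power, so there is no planned figure to reproduce. The check covers whether the laboratory route can be derived, and how much one event matters.

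**1. Are Hb and LDH measured together?** Inputs: Protocol Table 8-1 (hematology and both chemistry rows) and Table 8-5 (LDH is in both the full and the abbreviated panel). Full hematology is scheduled at every Core visit. The full and abbreviated chemistry rows together also cover every Core visit. At the screening confirmation visit, Hb and LDH alone are taken. Both values are therefore scheduled at all 14 columns of the table.

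**2. Is there enough history at each visit?** The hemoglobin limb needs one earlier Hb, and the LDH criterion needs two earlier LDH values. By Day 7 there are three scheduled earlier values of each (screening, confirmation, Day 1). All 11 visits after Day 1 qualify: 11 × 40 = 440 participant-visits if everyone attends.

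**3. Is the hemoglobin wording programmable as it stands?** Not without a choice. Nominal gaps between Core visits from Day 1 are 6, 7, 14, 14, 14, 28, 28, 14, 14, 14 and 14 days. The 28-day gaps precede Days 84 and 112, where the previous scheduled value lies outside a 15-day window and only the comparison with the latest assessment can be used. With the ±3-day visit windows, a nominal 14-day gap can reach 14 + 3 + 3 = 20 days, so the same question can arise at other visits.

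**4. What cannot be derived?** The signs-and-symptoms limb needs the investigator. Events between visits depend on unscheduled samples. A derived count can supplement the CRF count but cannot replace it.

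**5. Scale of one event.** Assumption: 40 participants, each followed for 168 days.
- Patient-years: 40 × 168 / 365.25 = 18.4.
- Rate change per event: 1 / 18.4 = 0.054 per year, or 5.4 per 100 patient-years.

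| Events (assumed) | Rate per year | Exact Poisson 95% CI |
|---|---|---|
| 0 | 0.00 | 0.00 to 0.20 |
| 1 | 0.05 | 0.00 to 0.30 |
| 2 | 0.11 | 0.01 to 0.39 |
| 3 | 0.16 | 0.03 to 0.48 |
| 6 | 0.33 | 0.12 to 0.71 |

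If one of n true events is not entered and nothing is wrongly entered, the understatement is 1/n: 33% for n = 3 and 17% for n = 6. These counts are illustrations only.

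**The case against.** Several counter-arguments have force.

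- **The SAP matches the endpoint.** Protocol Table 2-1 defines it as occurrences reported from Day 1 to Day 168, and a count of reported events fits that. This stands: a derived count is an addition, and the CRF-based analysis is not an error.
- **Entry is not free opinion.** A reader might infer that the count is simply the investigator's view. Table 8-3 does not support that, because the LDH criterion is mandatory for every clinical event. What remains is the absence of a visible check on non-entry and wrong entry.
- **The direction of bias is not shown.** It is tempting to say that the rate is biased in the drug's favour. Missed events lower it, but the open-ended symptom limb also allows over-entry, and the documents hold no data on either. The net direction is unknown.
- **Signals survive elsewhere.** BTH also goes on the AE page, and central Hb and LDH are analysed as endpoints of their own. True, but the AE route depends on the same reporter, and neither feeds the BTH rate.
- **Data management may catch it.** Protocol 11.2 describes generic discrepancy queries. Protocol 11.3 requires full verification of data for primary variables and leaves other consistency checks to a monitoring plan that is not among the documents. A BTH-to-laboratory check may exist there, but nothing visible supplies one.
- **One event lies within sampling error.** For one event, 0.054 per year is small beside an interval reaching 0.30. This limits the importance of the point but does not remove a systematic omission.

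**Conclusion.** This is a worthwhile, low-cost improvement to one secondary endpoint. The BTH count comes only from a site-completed page in an open-label trial, and no visible analysis compares it, in either direction, with Hb and LDH values collected at every Core visit. Protocol 4.1's description of BTH as objectively laboratory-measured is therefore partly delivered: the criteria include laboratory values, but how completely and correctly they are applied is not verified.

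Each event is worth about 5.4 per 100 patient-years, assuming 40 participants with full 168-day follow-up. Any percentage understatement is illustrative. BTH has no success threshold, so the primary conclusion against 15% does not change. Redacted parts of the SAP are not counted as missing.

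**What to change.** In SAP 2.6.1.8 and Table 5-1:

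1. Add a programmed derivation of the hemoglobin route in Table 8-3 (Hb fall of at least 2 g/dL, with LDH above 1.5 times ULN and above the last two values). Use central data, with local values where central are missing, as SAP 2.6.3 already does for other laboratory endpoints.
2. State one reading of the hemoglobin comparison interval that covers the 28-day gaps before Days 84 and 112 and late visits elsewhere.
3. Reconcile derived events with the CRF page in both directions before database lock, and query mismatches.
4. Report, as a sensitivity analysis, the rate from CRF events plus unmatched derived events. Flag Hb falls within 30 days after a transfusion (the window SAP 2.6.1.3 already uses) and CRF events that do not meet the LDH criterion. This rate can only equal or exceed the CRF rate, so the flagged counts must be shown beside it.
5. Keep the CRF-based rate as the main analysis.

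The cost is some programming and a few queries, with no new samples or visits. Some derived events will be false positives as hemoglobin falls after a transfusion, and a transfusion can also mask a true fall.
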